Patients randomized to the Suprapatellar Landmark (SPL) group will receive the same procedure as the Suprapatellar Ultrasound Guided (SPUS) group., with the exception of the sham ultrasound. To accomplish this, the ultrasound probe will purposely be positioned in the transverse plane of the suprapatellar area but the ultrasound display will be positioned so that the patient cannot visualize the screen, and the "FREEZE" button will be activated so that no active image is transmitted. The display will be positioned such that visualization by the patient will not be possible. The injecting physician will insert the needle lateral to the vastus lateralis toward the suprapatellar pouch. When the injecting physician believes the needle tip is in the pouch, the viscosupplement will be injected followed by the contrast.

It should be noted, that none of the participants in the study will be given the ability to visualize the ultrasound screen or injection procedure.

- 5. Following each injection, all patients will conclude their encounter with the injecting physician by being asked to rate on a scale of 0 to 10 their procedural pain from the procedure. For pain, a score of 0 will correspond to no pain and 10 will correspond to the worst pain they have ever experienced. After each injection, and at the three month follow up telephone call, the subjects will be asked to rate their overall procedure satisfaction on a 0-10 scale where "0" represents complete dissatisfaction and "10" represents complete satisfaction.
- 6. After the third injection, and after answering these questions, the patient will proceed directly to the Radiology Department.
- 7. Images of the joint will be obtained following the third injection. These images will be analyzed by a radiologist blinded to the technique employed and used to determine presence of or absence of the contrast medium within the joint.

Appointment 4 (telephone)

8. Subjects will be contacted approximately three months after the procedure by a Surveyor and the WOMAC Osteoarthritis Index will be repeated. The patients will be asked to rate their procedural satisfaction and also detail other therapies they have employed since the injection. This will include supplements, exercise (frequency and duration), acupuncture, physical therapy, etc.

Data Collection

Data collection will occur at three points during the investigation:

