• Initial evaluation: Screening instrument for first visit (history and physical, diagnostic and inclusion/exclusion criteria), WOMAC (prior to receiving each of the three injections), and intervention

The clinical staff will collect the following data:

- Name, email, phone number
- Demographics: age, gender, type and number of injections received previously
- Informed consent/HIPAA document
- WOMAC Osteoarthritis Index
- Post Procedure

The Injecting physician will record the following data:

- Group Assignment
- Amount and type of therapeutic substance injected
- Total time to complete procedure from sterilization to bandaging
- Procedural Pain Score (0 to 10)
- Procedural Satisfaction Score (0 to 10)
- Complications

In a separate electronic database, the radiologist will record the following data:

- Name
- Presence or absence of contrast material within the knee joint
- Three months after intervention (telephone)
 - WOMAC Osteoarthritis Index
 - Procedure Satisfaction Score (0 to 10)

Study Time Line

Assessment					
Study Day /	Initial Evaluation	and	Second	Third Injection	3 months
Period	First Injection		Injection	With contrast	Post Treatment
Screening	Х				
Informed	Х				
Consent, discuss					
Plan, etc.					
Randomization	Х				
Demographics,	Х				
History &					
Physical					
WOMAC (pre	х		Х	Х	Х
injection)					
Treatment	X		Х	Х	
Procedural Pain	Х		Х	Х	
(post injection)					
Procedural	Х		Х	X	Х

Satisfaction (post injection)			
Fluoroscopic Analysis		Х	
Complications (post injection)		X	

Statistical Consideration

Primary endpoints are presence/absence of contrast medium in the joint, the WOMAC osteoarthritis index, and overall satisfaction with the injection technique. Our statistical analysis of the WOMAC index will consider a mean change from baseline to post-injection with the variables of pain, stiffness, and function. We will also study the mean change of the Global Score from the WOMAC.

Data Analysis

Statistical analysis of the WOMAC score will consist of one-way analysis of variance (ANOVA) followed by Tukey's post-hoc multiple comparisons between the four groups with a 5%, two-sided familywise significance level (which allows for comparisons between all possible pairs of treatments). Chi square tests will be used to compare the percent accuracy among the four groups. We will also perform sub-analysis to determine if any trends can be linked to the type of medication (viscosupplementation) injected versus accuracy.

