Safety Monitoring and Analysis Plan

Since treatments are provided at the onset of the study, "stopping rules" will not apply in this study. Since the primary outcome includes pain and functioning at baseline and 3 months following the intervention, the entire study must be carried out in order to gather the desired data. There have been no unexpected side effects other than local pain and swelling at the injection site that have been reported in the studies using these injection techniques, so we do not believe any other specific side effects will need to be monitored. Patients will not be included in the study if a contraindication applies to them. Of note, viscosupplementation is not contraindicated in pregnant patients.

Sample Size Estimation

For the comparison of accuracy, a two group chi square test with a 5% two-sided significance level will have 80% power to detect a difference of 33 percentage points between groups when the accuracy in the less-accurate condition is 60% and the sample size in each group is 25.

Previous studies have demonstrated an effect size of the WOMAC ranging from 0.5 to 1.0 when medication interventions were studies on patients with knee pain. A sample size of 25 in each group will have 80% power to detect an effect size of 0.809 using a two group t-test with a 5% two-sided significance level.

Reference: Lenth, R. V. (2006-9). Java Applets for Power and Sample Size [Computer software]. Retrieved November, 2010, from http://www.stat.uiowa.edu/~rlenth/Power.

Reporting Adverse Events

Definitions:

Adverse events (adverse effects, adverse reactions): any occurrence of injury, dysfunction, disease, or abnormality of any organ or tissue that occurs in a subject enrolled in a clinical protocol. Manifestations of an adverse event may include symptoms, physical exam abnormalities, diagnostic study abnormalities, and/or death.

Expected adverse events: adverse events previously known or anticipated to result from: 1) the interventions and interactions used in the research (these events must be included as potential risks in the consent form); 2) the collection of identifiable private information under research (these events must be included as potential risks in the consent form); 3) an underlying disease, disorder, or condition of the human subjects; and/or 4) other circumstances unrelated to the research or any underlying disease, disorder, or condition of the subject.

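### The unblinded injecting physician records the post-injection pain and satisfaction scores, and satisfaction is a primary endpoint with no stated time point; a card the patient fills in alone would cheaply reduce operator influence

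*Combined protocol and SAP*

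**What the plan says.** - **Who knows the group.** Study Design and Methodology/Technical Approach both say that the injecting physician is not blinded. Patients are blinded to ultrasound use, and the radiologist and the 3-month Surveyor are blinded to group.
- **Who records.** Under Data Collection, "The Injecting physician will record the following data" introduces a list with group assignment, the procedural pain score and "Procedural Satisfaction Score (0 to 10"). A separate list, "The clinical staff will collect the following data", covers the WOMAC and demographics. The blinding of those staff is not described.
- **How the scores are obtained.** In Study Methodology/Procedures, step 5, "all patients will conclude their encounter with the injecting physician by being asked to rate on a scale of 0 to 10 their procedural pain". In the same step, after each injection and at the 3-month call, "the subjects will be asked to rate their overall procedure satisfaction on a 0-10 scale"; who asks is not stated. Step 8 has the Surveyor take the 3-month satisfaction rating.
- **Role of the scores.** Statistical Consideration: "Primary endpoints are presence/absence of contrast medium in the joint, the WOMAC osteoarthritis index, and overall satisfaction with the injection technique". No time point is given for satisfaction. Procedural pain is not listed as a primary endpoint.
- **A partial pointer on timing.** Safety Monitoring and Analysis Plan: "Since the primary outcome includes pain and functioning at baseline and 3 months following the intervention". Satisfaction is not mentioned there.

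Nothing in the protocol provides for self-completion or blinded recording of either score just after an injection.

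**The concern.** An outcome that passes through someone who knows the allocation can be shaped by that knowledge. Here the operator has just carried out the assigned technique, and records the patient's rating of it alongside the group assignment. An operator who expects one technique to do better could word the question, react to the answer or write the number down differently by group.

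The plan gives a plausible source for such an expectation. Medical Application hypothesises that ultrasound guidance raises accuracy and should improve patient-oriented results. Background and Significance cites an aspiration study with less pain under ultrasound guidance (3.71 versus 5.19 on a 10-cm scale). This shows a possible route and is not evidence that bias occurs.

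Only influence that differs between groups matters. Politeness towards the operator would act in all four arms and creates no group difference by itself. If the post-injection satisfaction ratings are primary, the exposure reaches a primary comparison. If not, it is confined to procedural pain and the non-primary satisfaction ratings.

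**Working it through.** **No figure in the plan to reproduce.** Sample Size Estimation covers only accuracy and the WOMAC, and Data Analysis states no method for satisfaction or procedural pain. The check is therefore a comparison of sections, a count of exposed ratings and one labelled illustration.

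**1. Who handles each patient-reported or image-based outcome**

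| Outcome | Recorded or collected by | Blinded? |
|---|---|---|
| Contrast in joint | Radiologist, separate database | Yes |
| WOMAC before each injection | Clinical staff | Not described |
| WOMAC and satisfaction at 3 months | Surveyor | Yes |
| Pain and satisfaction after each injection | Injecting physician | No |

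The post-injection pain and satisfaction scores are the only ones in this table assigned to someone known to be unblinded. For pain, step 5 places the question at the end of the encounter with that physician. For satisfaction, that the physician also asks is an inference from the recording duty.

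**2. Which satisfaction ratings are primary**

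Step 5 uses one term for the ratings after each injection and at 3 months, and the Study Time Line puts all four in one row. The safety section ties pain and functioning to baseline and 3 months, which makes a 3-month reading of satisfaction plausible without settling it. Three readings remain open.

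**3. Ratings that pass through the unblinded recorder**

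Inputs: 120 allocations (Study Design) or 4 × 25 = 100 (Sample Size Estimation); satisfaction rated 3 times after injection and once at 3 months; pain rated 3 times; no dropout assumed.

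Share = operator-recorded primary ratings ÷ all primary ratings.

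| Primary satisfaction rating | N = 120 | N = 100 | Share |
|---|---|---|---|
| 3-month only | 0 / 120 | 0 / 100 | 0% |
| All four | (120 × 3) / (120 × 4) = 360 / 480 | 300 / 400 | 75% |
| Post-injection only | 360 / 360 | 300 / 300 | 100% |

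Procedural pain, not a listed primary endpoint: 120 × 3 = 360 of 360, or 300 of 300. These counts measure exposure and say nothing about the size of a bias.

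**4. Illustration under an assumption that is not in the documents**

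Suppose there is no true difference and operator influence alone shifts mean satisfaction between two groups by *b* standard deviations. A two-sided 5% t-test with *n* per group then has noncentrality *b*√(*n*/2) on 2*n* − 2 degrees of freedom. For *b* = 0.2 and *n* = 25 this is 0.2 × √12.5 = 0.71 on 48 degrees of freedom. The chance of a false-positive result is:

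| *b* (SD) | *n* = 25 | *n* = 30 |
|---|---|---|
| 0.1 | 6.4% | 6.7% |
| 0.2 | 10.7% | 11.9% |
| 0.3 | 18.0% | 20.8% |
| 0.5 | 41.0% | 47.8% |

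The documents support no particular value of *b*, including zero, so this table does not bear on severity.

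**5. Whether the planned blinding check would reveal the problem**

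Study Design asks subjects and radiologists to guess the group. That tests whether patients know their allocation. A patient who remains fully blinded could still be prompted differently, or have a score recorded differently, so the guesses would not detect it.

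**The case against.** The strongest reply is that the protocol contains no error here. An operator cannot be blinded to a needle technique, and the score belongs to the patient. The patient is protected by a hidden screen and, in the landmark groups, a frozen sham image. If the 3-month rating is the primary one, no primary satisfaction rating passes through the operator. Satisfaction is also absent from Objectives and Specific Aims and from the three questions under Scientific Justification, although that section does mention it as a patient-oriented outcome. A card cannot undo cues given during the injection, and the documents do not say whether staff are free afterwards.

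All of this stands as a limit on severity. Blinding the rater does not blind the recorder, however. The 3-month reading is plausible but unstated. That the card is only a partial remedy is a reason to claim a reduction in operator influence, not its removal. Staff availability is a real cost and is counted below.

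**Conclusion.** The point holds as a minor design weakness. An unblinded operator records both post-injection scores, and one of them may belong to a primary endpoint. The operator records 0%, 75% or 100% of the primary satisfaction ratings according to which time points are meant, assuming full enrolment and no dropout. Every procedural pain rating goes the same way, though pain is not a listed primary endpoint. The size and direction of any bias are unknown, and the documents give no evidence that it occurs. Two things rest on inference: that the physician asks for the satisfaction rating, and that post-injection satisfaction may be primary. If the sponsor confirms that only the 3-month rating is primary, the concern shrinks to procedural pain and the non-primary satisfaction ratings.

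**What to change.** 1. **Statistical Consideration:** state which satisfaction time point or points are primary.
2. **Data Collection:** remove the pain and satisfaction scores from the injecting physician's list.
3. **Study Methodology/Procedures, step 5:** once the physician has left, the patient completes both 0-10 items alone on a card and hands it to the clinical staff who already collect the WOMAC. If that staff member was in the room for the injection, the card goes into a sealed envelope. At the third visit this comes before imaging, which keeps the order in step 6: "After the third injection, and after answering these questions, the patient will proceed directly to the Radiology Department".
4. **Study Design:** state that these staff are not told the group. The randomisation envelope already goes unopened to the study doctor, so this fits the current process.

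**Cost:** one edited list, one sentence in each of three sections, and a two-item card. No visit or question is added, and sample size, significance level and treatment do not change. The ratings come a few minutes later, and a staff member must be at hand after each injection.

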1. Based on usual standard of care for knee pain, the treating physician will determine whether a series of viscosupplemental intra-articular knee joint injections is recommended. Patients who would likely benefit from the injections will be invited to participate in the study but will still receive usual care if they decide not to participate.

2. The informed consent document will be reviewed with and signed by interested patients.

Participants will complete the Western Ontario and McMaster Universities Arthritis Index (WOMAC), a validated, widely used instrument that measures self-reported pain, joint stiffness, and physical function. This index consists of 24 questions (5 pain, 2 stiffness, 17 physical function) and takes less than 5 minutes to complete. Raw scores are normalized to fit within a range of 0 (worst) to 100 (best). Additionally, there is a normalized raw Global Score that considers the variables of pain, stiffness, and physical function as a collective. The WOMAC will be issued four times during the study; prior to the three injections and again at the three month follow up phone call.

- 3. The injection procedure will be completed based on group assignment (see below). For the third injection in the series, all four groups will receive a "one needle, two syringe" injection as follows:
 - a. A 21 gauge two inch needle attached to a 5 ml syringe filled with 5 ml of Omnipaque 300 ® (General Electric Healthcare, Princeton, NJ) contrast medium will be introduced into the skin at the predetermined site and directed either with or without ultrasound guidance based upon group assignment. Injection site, landmarks, and intended path of the needle are detailed further in the group description below.
 - b. The entire contents of the syringe will then be injected. Following delivery of the contrast medium, the syringe will be removed while the needle remains in place.
 - c. A second syringe with the pre-determined medication (Hyaluronic Acid) will be attached to the needle and this medication will be delivered.
 - d. The needle and syringe will be removed from the knee and the injection will be bandaged.
- 4. The first and second injections will be performed based on the group assignment (see below) but will not include the use of contrast medium.

Group 1: Joint Line Ultrasound (JLUS)

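### Three primary endpoints, with WOMAC analysed as four scores, have no error control across them; if any one can be claimed at 5%, the false-positive rate is about 14% for three tests and roughly 16–23% for six

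*Combined protocol and SAP*

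**What the plan says.** Statistical Consideration names the endpoints: "Primary endpoints are presence/absence of contrast medium in the joint, the WOMAC osteoarthritis index, and overall satisfaction with the injection technique".

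The same section says the WOMAC analysis "will consider a mean change from baseline to post-injection with the variables of pain, stiffness, and function", and adds: "We will also study the mean change of the Global Score from the WOMAC". That makes four WOMAC scores, with none marked as the main one. The post-injection time is not tied to a visit there, although the safety section refers to baseline and 3 months.

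Data Analysis prescribes a one-way ANOVA and Tukey comparisons for WOMAC "with a 5%, two-sided familywise significance level (which allows for comparisons between all possible pairs of treatments"). Accuracy is to be compared among the four groups by chi-square tests, with no level given in that section and no adjustment for pairs. The 5% level for accuracy appears only under Sample Size Estimation.

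For satisfaction, item 5 of the study procedures says: "After each injection, and at the three month follow up telephone call, the subjects will be asked to rate their overall procedure satisfaction". That is four ratings. No test, significance level, power statement or primary time point is given for it.

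The plan contains no hierarchy, no division of alpha, and no rule on whether one or all of the primary endpoints must succeed.

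**The concern.** A trial with several primary endpoints must say either that all must succeed or how the error rate is shared among them. This plan says neither. A significant result on accuracy, on any of four WOMAC scores or on satisfaction could therefore be reported as a primary finding. The only multiplicity adjustment works inside one WOMAC score and gives no protection against choosing among scores or endpoints. At stake is whether a reported primary result carries a 5% false-positive risk or one two to four times as high.

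**Working it through.** **1. The plan's own figures.** Sample Size Estimation gives 25 per group, 5% two-sided and 80% power.

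- Accuracy, 60% against 60 + 33 = 93%, mean rate 0.765. Power = Φ[(0.33 − 1.96 × √(2 × 0.765 × 0.235 / 25)) / √((0.60 × 0.40 + 0.93 × 0.07) / 25)] = Φ[(0.33 − 0.235) / 0.1105] = 80.5%.
- WOMAC, effect size 0.809, two-sample t-test: 80.0%.

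Both reproduce. Each uses the full 5% for a single comparison of two groups.

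**2. Independent tests at 5%.** With k tests and no true difference, P(at least one significant) = 1 − 0.95^k.

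- k = 2: 9.75%
- k = 3: 14.3%
- k = 6: 26.5%

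The last figure is only a bound. The study procedures state that "there is a normalized raw Global Score that considers the variables of pain, stiffness, and physical function as a collective", so the four WOMAC tests cannot be independent.

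**3. Correlated tests.** The documents give no correlations, so these are assumptions shown over a range. Each row is 20,000 simulated trials with no true difference and four groups of 25. WOMAC scores and satisfaction are tested by one-way ANOVA, and accuracy by one four-group chi-square with a true rate of 77% in every group. Global is weighted by item count: (5 × pain + 2 × stiffness + 17 × function) / 24. Accuracy is uncorrelated with the other measures where the satisfaction–WOMAC correlation is 0, and otherwise weakly correlated with them (0.1 in size).

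| Subscale correlation | Satisfaction–WOMAC correlation | Accuracy, Global, satisfaction (3 tests) | All 6 tests | Accuracy, Global (2 tests) | Accuracy, four WOMAC (5 tests) |
|---|---|---|---|---|---|
| 0.5 | 0 | 14.4% | 21.9% | 9.6% | 17.5% |
| 0.5 | 0.3 | 13.8% | 21.0% | 9.7% | 17.5% |
| 0.7 | 0.3 | 14.2% | 19.9% | 9.8% | 16.0% |
| 0.8 | 0.5 | 13.4% | 17.8% | 9.5% | 14.6% |
| 0.9 | 0.5 | 13.9% | 16.9% | 9.8% | 13.1% |

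The simulation standard error at 20% is √(0.2 × 0.8 / 20,000) = 0.3 points. Other combinations within these ranges, with 25 or 30 per group, stayed within 16–23% for six tests. Even with uncorrelated subscales, six tests reached 23.7%, still short of 26.5%.

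**4. Accuracy alone.** The table assumes one overall chi-square. If the chi-square tests were run unadjusted on all six treatment pairs, accuracy alone would reach about 21–22%, and all tests together about 31–35%.

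**5. Cost of splitting alpha.** The first Holm step across three endpoints uses 0.05 / 3 = 0.0167. In the plan's own two-group scenarios, power at that level is 65.1% (accuracy) and 64.8% (WOMAC) with 25 per group, and 75.0% and 74.6% with 30.

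**The case against.** Several stronger readings are tempting, and the documents do not support them.

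- **A broken promise of 5%.** A reader might take the phrase "with a 5%, two-sided familywise significance level" as a commitment for the whole trial. The same sentence limits it to pairs of treatments in the WOMAC analysis. The plan is silent across endpoints; it does not contradict itself.
- **An error rate of 26%.** That needs six independent tests, which is impossible when Global is built from the other three scores.
- **Every endpoint tested at 5%.** This is documented for WOMAC and, through the sample-size section, for accuracy. For satisfaction it is an assumption.
- **Two conflicting definitions of what is primary.** The safety section says "Since the primary outcome includes pain and functioning at baseline and 3 months following the intervention". The sentence explains why stopping rules do not apply, and saying that the outcome includes pain and function is compatible with a list that contains WOMAC.

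The most serious objection is that no success rule is stated. If all three endpoints had to succeed, there would be no inflation. It can also be argued that needle placement and patient outcome are separate questions that need not share one alpha. The condition must therefore stay attached to the figures. Still, the plan's structure points to separate claims: Scientific Justification poses three questions, all labelled primary, and accuracy and WOMAC are each powered at 80% at the full 5%. If both had to succeed, joint power under independence would be 0.80 × 0.80 = 64% before satisfaction is counted, and the plan mentions no such requirement.

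It is also fair to say that making WOMAC secondary demotes a question the plan calls primary. That is a real cost of the fix.

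**Conclusion.** The concern holds as an omission: three primary endpoints, four WOMAC scores and no error control across them. The size depends on two assumptions, that any one significant result counts as a primary finding and that each test is run at 5%. On that footing the false-positive rate is about 14% for three tests. For six it is roughly 16–23%, with assumed subscale correlations of 0.5–0.9 and satisfaction–WOMAC correlations of 0–0.5. Leaving satisfaction out, because it has no stated test, still gives about 10% with one WOMAC score and about 13–17% with four. Choosing freely among the four satisfaction ratings, or testing accuracy pair by pair without adjustment, would add to these figures.

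**What to change.** - **Primary:** contrast in the joint at the third injection. It is the subject of aims 1 and 2 and is read by a blinded radiologist. Test it with one overall four-group chi-square at 5%, and adjust the pairwise tests for multiplicity.
- **Key secondary:** change in WOMAC Global Score from baseline to 3 months, tested at 5% only if the overall accuracy test is significant. Tukey stays for treatment pairs within that score.
- **Supportive:** WOMAC pain, stiffness and function, and 3-month satisfaction, as estimates with 95% intervals.

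This fits Scientific Justification, where patient-reported outcomes supplement the accuracy conclusion. It needs protocol and SAP wording only, with no division of alpha between endpoints. The downside is that an isolated WOMAC or satisfaction result cannot be claimed as confirmed, and WOMAC is not formally tested if accuracy misses.

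The stated 80% applies to one unadjusted two-group comparison, so power for the overall test and the adjusted pairs should be stated too. For example, Bonferroni over six pairs uses 0.05 / 6 = 0.0083, where power for 60% against 93% is about 55% with 25 per group and 66% with 30.

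If all three must stay primary, use Holm across accuracy, WOMAC Global and 3-month satisfaction. Specify the satisfaction test and restate power: about 65% with 25 per group and about 75% with 30 at the first Holm step, against the stated 80%.

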- **a.** There will be a Research Coordinator at the trial site who will administer the consent and HIPAA authorizations. This will be performed with a standardized consent form (Appendix A), including a scripted discussion of the study procedures and a scripted discussion of risks inherent in the injection techniques
- **b.** Upon completion of consent, the Coordinator will have the subject explain their understanding of the concept of treatment in their own words to ensure the subjects understand the consent.

Study Design

The study will be a randomized, double-blinded clinical study comparing four techniques for intra-articular knee injections.

The study investigators will receive a list of 120 computer generated random numbers from

Page 8 of 17 Version 2.0 one to four. No more than 30 will be in each group to ensure that each group is the correct size. Upon entry into the study, and prior to the first injection, subjects will randomized by selecting a sealed envelope from a box containing an equal number of envelopes for each of the four treatments groups. The envelope will be given, unopened, to the study doctor. The subject will be blinded to their study group assignment.

Double-blinding will be done as follows: The subjects will be blinded to whether ultrasound was used to guide their treatment. The radiologist, who will review the fluoroscopic images after the injections, will be blinded to treatment group assignment. The injecting physician will not be blinded to the treatment group assignment. Treating physicians (injecting physicians) will perform the technique as detailed below based on the assignment of the participant. Subjects and the radiologists will both be asked to guess their treatment group at each point in the data collection to determine the effectiveness of the blinding process. The Surveyor will also be blinded to the treatment group allocation.

The injecting physicians will consist of orthopedic surgeons, sports medicine fellows, or sports medicine fellowship trained primary care physicians. All injecting physicians will receive a minimum of 2 hours of hands-on training specific to the procedures employed in this study. Additionally, they will be supervised for their first several ultrasound-guided procedures to assure competence with the techniques.

Study Methodology/Procedures

Appointment 1

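### WOMAC change is compared by one-way ANOVA with no baseline covariate: a valid test, but generally less precise than a baseline-adjusted one and sensitive to chance baseline imbalance

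*Combined protocol and SAP*

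**What the plan says.** Statistical Consideration lists WOMAC among three primary endpoints and defines the quantity analysed: "Our statistical analysis of the WOMAC index will consider a mean change from baseline to post-injection". This covers the pain, stiffness and function scores, and the Global Score is treated the same way. Data Analysis gives the test: "Statistical analysis of the WOMAC score will consist of one-way analysis of variance (ANOVA"), followed by Tukey comparisons of all pairs of the four groups at a two-sided 5% familywise level. Group is the only term, and no covariate appears there or elsewhere.

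The baseline value is already collected. Study Methodology/Procedures states: "The WOMAC will be issued four times during the study", that is, before each injection and at the 3-month call. Safety Monitoring and Analysis Plan points to the time points of interest: "Since the primary outcome includes pain and functioning at baseline and 3 months following the intervention".

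Study Design describes allocation by "selecting a sealed envelope from a box containing an equal number of envelopes for each of the four treatments groups". This balances group size (at most 30 each, 120 in total) and nothing else. Sample Size Estimation claims, for 25 per group, "80% power to detect an effect size of 0.809 using a two group t-test", also without a baseline term.

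**The concern.** A change score is a baseline adjustment with the slope set to 1. When the true slope differs from 1, the change score over- or under-corrects, and the residual dependence on baseline stays in the error. Two consequences follow from this one mechanism. Averaged over randomisations, the standard error is larger than it need be. Within the trial actually run, the estimated difference shifts with whatever baseline gap chance produced; at a slope below 1, regression to the mean favours the group that started worse.

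Both matter more when groups are small, allocation is not stratified on severity, and there are six pairwise comparisons. Eligibility (age 18 to 90, clinician-determined need for injection) also makes a wide spread of baseline scores plausible.

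**Working it through.** **Inputs from the documents.** Four groups; 25 per group (Sample Size Estimation) or 30 (Study Design); effect size 0.809; Tukey at 5% two-sided familywise.

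**Assumptions.** The documents give neither rho nor the ratio k of follow-up SD to baseline SD. I show rho from 0.3 to 0.9 and k of 0.8, 1 and 1.3, with baseline SD set to 1 and a common slope.

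**1. The plan's own figure.** Two-group t-test, n = 25, d = 0.809, noncentrality 0.809 × √(25/2) = 2.860, 48 df: power 80.03%. The stated 80% reproduces.

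**2. The planned test.** Tukey's critical value for one pair is q/√2 with 4n − 4 df: 2.615 at n = 25 and 2.607 at n = 30. Power for one pair at d = 0.809 is 59.8% and 70.0%. These are the starting points below.

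**3. Variance per observation.**
- Change score: 1 + k² − 2·rho·k
- ANCOVA: k²(1 − rho²), times 1 + 1/(4n − 6) for estimating the slope (1 + 1/94 = 1.011 at n = 25)
- Difference before that slope cost: (1 − rho·k)², never negative, and zero at rho = 1/k

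At k = 1 the ratio is (1 − rho²)/(2(1 − rho)) = (1 + rho)/2.

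**4. Power for one Tukey pair, k = 1, with 0.809 in change-score SD units.** The noncentrality is divided by the square root of the ratio, including the slope cost; df are 4n − 5.

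| rho | variance ratio | cut | cut after slope cost | power, n = 25 (from 59.8%) | power, n = 30 (from 70.0%) |
|---|---|---|---|---|---|
| 0.3 | 0.65 | 35% | 34% | 81.7% | 89.4% |
| 0.5 | 0.75 | 25% | 24% | 74.7% | 83.8% |
| 0.7 | 0.85 | 15% | 14% | 68.1% | 78.0% |
| 0.9 | 0.95 | 5% | 4% | 62.0% | 72.3% |

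Simulation at n = 25 (40,000 trials per cell) gives 81.7%, 74.6%, 68.3% and 62.0%.

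**5. If 0.809 is in single-time-point SD units instead** (n = 25, k = 1), power goes from 43% to 64%, 60% to 75% and 86% to 91% at rho 0.3, 0.5 and 0.7. At rho 0.9 it is 99.99% either way.

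**6. Unequal variances, n = 25, change-score SD units** (cuts before slope cost; power from 59.8%).

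| rho | cut, k = 1.3 | power, k = 1.3 | cut, k = 0.8 | power, k = 0.8 |
|---|---|---|---|---|
| 0.3 | 19% | 71.0% | 50% | 91.7% |
| 0.5 | 9% | 64.2% | 43% | 87.2% |
| 0.7 | 1% | 59.7% | 37% | 83.3% |
| 0.9 | 8% | 63.9% | 39% | 84.7% |

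At k = 1.3 the gain vanishes at rho = 1/1.3 = 0.77.

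**7. Chance imbalance.** The expected range of four standard normal values is 2.059. The largest gap between any two baseline means therefore averages 2.059/√25 = 0.41 SD at n = 25 and 2.059/√30 = 0.38 SD at n = 30. At k = 1 a gap shifts the change-score difference by (1 − rho) times its size: 0.41 × 0.5 = 0.21 SD at rho 0.5, and 0.41 × 0.3 = 0.12 SD at rho 0.7, with no treatment effect. In simulation at n = 25 the change-score difference correlates −0.59, −0.50 and −0.39 with the baseline difference at rho 0.3, 0.5 and 0.7. For the adjusted difference the correlation is about 0.

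**8. Validity.** Simulated familywise error at n = 25 and 30 is 4.8% to 5.1% for the planned change-score Tukey and 4.7% to 5.2% for Tukey on adjusted means. Both hold 5%.

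**The case against.** The strongest reply is that nothing is broken. The planned test is valid, already uses baseline through the change score, and controls the familywise error. What remains is a choice between two legitimate analyses, with a gain that depends on two unstated quantities and can be close to nil. That is right, and it limits the point to efficiency.

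The 60% starting power comes largely from a separate mismatch: the trial was sized on an unadjusted t-test but will be analysed with Tukey. On the t-test basis, power would go from 80.0% to 93.5%, 89.9%, 86.0% and 82.0% at rho 0.3, 0.5, 0.7 and 0.9 (equal variances), so the gain is 2 to 13 points rather than 2 to 22. Both sets are correct; the Tukey figures describe the test the plan will run.

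The 0.41 SD gap is the largest of six. For one pair named in advance, the expected absolute gap is √(2/25) × √(2/π) = 0.23 SD, and the shift is about 0.11 SD at rho 0.5 and 0.07 SD at rho 0.7. The change-score standard error already contains this variation, and Tukey allows for picking the extreme pair. Imbalance and lost precision are therefore one problem seen conditionally and on average, and should not be counted twice.

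The Data Analysis sentence refers to the WOMAC score, not its change. If raw 3-month scores were meant, baseline would go unused, the variance ratio would be 1 − rho² (0.91, 0.75, 0.51 at rho 0.3, 0.5, 0.7), and the same remedy would apply.

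Finally, naming 3 months settles a visit that Statistical Consideration leaves as post-injection. That is a second decision. Safety Monitoring and Analysis Plan supports it for pain and functioning; the sponsor should confirm it for stiffness and the Global Score.

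**Conclusion.** The point holds as a recommended improvement, not as a defect in validity. The planned comparison keeps its error rate and is unbiased on average, but it is generally less precise than an analysis that estimates the baseline slope. With equal variances and rho from 0.3 to 0.7, the net variance reduction at 25 per group is 34% to 14%; at rho 0.9 it is 4%. If follow-up scores are more variable than baseline the gain can shrink to nothing, and if they are less variable it can be larger. Across the scenarios examined, the worst result is break-even (59.7% against 59.8%). These figures rest on assumed rho, variance ratio and a common slope. Confidence in the size is therefore moderate; the direction does not depend on those values, apart from the slope cost of about 1% of variance.

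**What to change.** In Data Analysis, replace the WOMAC sentence with text to this effect: each 3-month WOMAC score (pain, stiffness, function, global) will be analysed by ANCOVA with the four-level treatment group and that score's value before the first injection as covariate; Tukey comparisons of the adjusted means will be made at the 5% two-sided familywise level, with 95% confidence intervals; change from baseline will be reported descriptively.

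If the sponsor prefers to keep change as the outcome, adding the baseline score as a covariate gives identical group contrasts. State explicitly that 3 months is the analysis time point for all four scores.

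The cost is one sentence, one degree of freedom and about 1% of variance for estimating the slope. No new data or visits are needed. The covariate should be fixed before unblinded data are seen.
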